### **6.2.1 Drug accountability**

A Drug Accountability form will be used to record study medication dispensing and return information on a by-participant basis and will serve as source documentation during the course of the study. Details of any study medication lost, damaged (due to breakage or wastage), not used, partially used, disposed of at the study site, or returned to the Sponsor or designee must also be recorded on the appropriate forms. All supplies and pharmacy documentation must be made available throughout the study for UCB (or designee) to review.

The Investigator (or designee) is responsible for retaining all used, unused, and partially used containers of study medication until returned or destroyed.

The Investigator may assign some of the Investigator's duties for drug accountability at the study site to an appropriate pharmacist/designee.

The Investigator must ensure that the study medication is used only in accordance with the protocol.

Periodically, and/or after completion of the clinical phase of the study, all used (including empty containers)/partially used, unused, damaged, and/or expired study medication must be reconciled and either destroyed at the site according to local laws, regulations, and UCB Standard Operating Procedure or returned to UCB (or designee). Investigational medicinal product intended for the study cannot be used for any other purpose than that described in this protocol.

### **6.3 Measures to minimize bias**

This is an open-label study.

At Screening, each study participant will be assigned a unique 5-digit study participant number from a range of numbers supplied by UCB Clinical Data Operations, Technology, and Standards.

### **6.4 Treatment compliance**

Study participant compliance will be ensured by the administration of study medication by designated site personnel. Drug accountability must be recorded on the Drug Accountability form.

### **6.5 Concomitant medication(s)/treatment(s)**

#### **6.5.1 Permitted concomitant treatments (medications and therapies)**

The following concomitant medication is permitted during the study:

- Paracetamol for the treatment of mild symptoms (eg, headache or other pain), given at most every 6 hours to 8 hours, not exceeding 2g/day, and with a total of no more than 5g over 7 days.

#### **6.5.2 Prohibited concomitant treatments (medications and therapies)**

The following concomitant medications are prohibited during the study:

- With the exception of permitted concomitant treatments listed in Section 6.5.1, all prescription or nonprescription medicines are prohibited within 2 weeks or 5 half-lives whichever is longer of the respective drug prior to first administration of PSL and during the clinical part of the study unless required to treat an AE. This includes all over-the-counter remedies, vitamins and herbal, and dietary supplements (including St. John's Wort).
  - Hepatic enzyme-inducing drugs (eg, glucocorticoids, phenobarbital, isoniazid, phenytoin, rifampicin, etc.) should not be used within 2 months prior to dosing. In case of uncertainty, the Medical Monitor should be consulted.
- Drugs of unknown half-lives are prohibited within 2 weeks before administration of PSL and during the clinical part of the study, unless required to treat an AE.

If a study participant needs or takes any prohibited medication, the Investigator will (where possible) discuss with the Sponsor Study Physician and a decision will be made whether the study participant can continue in the study or must be withdrawn.

### **6.5.3      Rescue medication**

Not applicable.

### **6.6      Dose modification**

No PSL dose modifications are permitted during the study for an individual study participant unless necessary to protect study participant's safety or well-being.

### **6.7      Treatment after the end of the study**

There are no plans for continued study participant care or treatment after the end of the study.

## **7            DISCONTINUATION OF STUDY MEDICATION AND PARTICIPANT DISCONTINUATION/WITHDRAWAL**

### **7.1      Discontinuation of study medication**

Study medication will be stopped if the study participant develops a medical condition (or laboratory abnormality or ECG change) that, in the opinion of the Investigator, compromises the study participant's ability to participate or compromises the study participant's safety.

[figure not shown]
In all cases the study participant should be followed until the condition has resolved as agreed by the Investigator and the UCB Study Physician. If a study participant discontinues study medication, no restart will be allowed.

#### **7.1.1      Liver chemistry stopping criteria**

Discontinuation of study medication for abnormal liver function should be considered by the Investigator when a study participant meets 1 of the conditions outlined in [Figure 7-1](#) or if the Investigator believes that it is in best interest of the study participant.

Study medication will be discontinued immediately and permanently for a study participant if liver chemistry stopping criteria are met.

**Figure 7-1: Liver chemistry stopping algorithm**

ALT=alanine aminotransferase; AST=aspartate aminotransferase; INR=international normalized ratio; SAE=serious adverse event; ULN=upper limit of normal

Specific assessments and follow up actions for potential drug-induced liver injury (PDILI) are provided in Appendix 6 (Section 10.6).

### 7.1.2 Criteria for study hold/stopping due to adverse events

In recognition of the advanced status of the development program for PSL, the following study hold/stopping rules will apply to this study.

In the event that either or both of the following criteria are met, a safety review will be immediately initiated:

- The occurrence of a serious adverse reaction (SAR) (ie, an SAE considered at least possibly related to the study medication) in 2 study participants, where those SARs occur in the same body system.
- The occurrence of a severe nonserious adverse reaction (ie, severe nonserious AEs considered at least possibly related to the study medication) in 3 study participants, where those severe adverse reactions:
  - Occur in the same body system, and
  - Lead to withdrawal of the affected participant

The safety review will be conducted by an internal, study-specific Safety Monitoring Committee comprised of the Investigator and appropriate members of the UCB Study Team (such as the Study Physician, Safety Physician, Clinical Project Manager, and Clinical Pharmacologist), as quickly as possible, to review the available data and determine whether it is appropriate to continue dosing at the next scheduled dosing point. This will take the form of a risk/benefit

evaluation from the perspective of the individual study participants. In making this evaluation, account will be taken of the potential risks of sudden discontinuation of study medication, particularly in participants who may be taking higher dose levels, and whether or not a tapering period, and its duration/speed, should be undertaken.

The Safety Monitoring Committee will also decide whether it is appropriate to continue the study with or without dose adaptations, additional safety assessments, or other changes in design. If such changes are deemed necessary to protect the wellbeing of participants, further dosing in the study will be suspended while a substantial amendment is submitted to the Country(ies) Health Authority and Research Ethics Committee(s), and the study will not restart until that amendment has been approved.

If the Safety Monitoring Committee cannot be convened before the next scheduled dosing point, the Investigator will make an independent evaluation as to whether it is appropriate to continue dosing pending the review.

Detailed procedures for reporting SAEs and other safety events which may meet study hold/stopping criteria, are provided in Appendix 3 (Section 10.3).

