#### **8.6 Safety signal detection**

Selected data from this study will be reviewed periodically to detect as early as possible any safety concern(s) related to the study medication so that investigators, clinical study participants, regulatory authorities, and IRB/IECs will be informed appropriately and as early as possible.

The UCB Study Physician or medically qualified designee/equivalent will conduct an ongoing review of SAEs and perform ongoing SAE reconciliations in collaboration with the PS representative.

As appropriate for the stage of development and accumulated experience with the study medication, medically qualified personnel at UCB may identify additional safety measures (eg, AEs, vital signs, laboratory, or ECG results) for which data will be periodically reviewed during the course of the study.

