#### Assessment of Intensity

The Investigator will make an assessment of intensity for each AE and SAE reported during the study and assign it to 1 of the following categories:

- Mild: An event that is easily tolerated by the study participant, causing minimal discomfort and not interfering with everyday activities.
- Moderate: An event that causes sufficient discomfort and interferes with normal everyday activities.
- Severe: An event that prevents normal everyday activities. An AE that is assessed as severe should not be confused with a SAE. Severe is a category utilized for rating the intensity of an event; and both AEs and SAEs can be assessed as severe.
- An event is defined as 'serious' when it meets at least 1 of the predefined outcomes as described in the definition of an SAE, NOT when it is rated as severe (eg, a severe AE may be either serious or not serious, depending on whether these criteria are also met).

The National Cancer Institute Common Terminology Criteria for Adverse Events should be used as a supportive standardization instrument to evaluate AEs and SAEs but the final intensity grading by the Investigator must be mild, moderate, or severe.

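### Section 7.1.2 does not require a safety review when three severe related same-body-system reactions lead to withdrawal and exactly one of them is serious

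*Protocol*

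**What the plan says.** Protocol Section 7.1.2 sets two criteria and states that when "either or both of the following criteria are met, a safety review will be immediately initiated".

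- The first is "The occurrence of a serious adverse reaction (SAR) (ie, an SAE considered at least possibly related to the study medication) in 2 study participants". Both reactions must fall in one body system; neither severe intensity nor withdrawal is required.
- The second is "The occurrence of a severe nonserious adverse reaction (ie, severe nonserious AEs considered at least possibly related to the study medication) in 3 study participants". Those reactions must also share a body system and "Lead to withdrawal of the affected participant".

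The second criterion is restricted to nonserious events both in its opening phrase and in its parenthetical definition. Nothing in the section adds a case from one criterion to the count of the other.

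Appendix 3 (Section 10.3.1, Assessment of Intensity) treats intensity and seriousness as separate attributes: "a severe AE may be either serious or not serious, depending on whether these criteria are also met".

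Outside Section 7.1.2, the study physician or designee "will conduct an ongoing review of SAEs and perform ongoing SAE reconciliations" (Section 8.6).

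**The concern.** A safety trigger should not become harder to meet as the same set of cases gets worse, and this one does. Three severe nonserious withdrawals in one body system start the review by rule. If one of those three reactions also meets a seriousness criterion, it leaves the count of three, and on its own it is too few for the serious count.

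The mixture is plausible for this drug. Section 2.3 says that adverse events are mainly central nervous system effects. It also reports acute psychiatric serious events in two healthy participants, early after starting or stopping padsevonil without titration or taper. Here a 200 mg dose is given on Day 1 without titration. Serious and severe nonserious reactions could therefore fall in the same body system.

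At stake is whether the Safety Monitoring Committee must convene and decide on further dosing in healthy volunteers who have no medical benefit from taking part. In this one case that step depends on discretion.

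**Working it through.** The documents state no figure for how the rule performs, so the check is an enumeration followed by an illustrative probability.

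**Inputs from the Protocol.** The review starts on either criterion. The thresholds are 2 participants (serious) and 3 participants (severe nonserious). A severe event may be serious or not. Planned enrolment is N = 39.

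**Step 1: the rule as written.** Consider participants who each have one severe, related reaction in the same body system that leads to withdrawal. Let s be the number whose reaction is serious and n the number whose reaction is nonserious.

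- Current rule: review if s ≥ 2 or n ≥ 3.
- Rule with all severe reactions counted in the second criterion: review if s ≥ 2 or s + n ≥ 3.

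| Affected | s | n | Current rule | All severe counted |
|---|---|---|---|---|
| 3 | 0 | 3 | review | review |
| 3 | 1 | 2 | **no review** | review |
| 3 | 2 | 1 | review | review |
| 3 | 3 | 0 | review | review |
| 4 | 0 to 4 | 4 to 0 | review in every case | review in every case |

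Over all (s, n) with s + n ≤ 39, the two rules differ only at (1, 2). From (1, 2), the next like case gives (2, 2) or (1, 3), and both meet the current rule.

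**Step 2: share of three-case clusters that fall in the gap.** Let q be the assumed share of such reactions that are serious. Given exactly three affected participants, P(exactly one serious) = 3q(1−q)².

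- q = 0.1: 3 × 0.1 × 0.81 = 0.243
- q = 0.2: 3 × 0.2 × 0.64 = 0.384
- q = 1/3: 3 × 1/3 × 4/9 = 0.444
- q = 0.5: 3 × 0.5 × 0.25 = 0.375

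**Step 3: chance that the study ends in the gap.** Let p be the assumed probability that a participant has such a reaction in a given body system, independently across participants. Then

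P(gap) = C(39,3) p³ (1−p)³⁶ × 3q(1−q)², with C(39,3) = 39 × 38 × 37 / 6 = 9139.

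For p = 1%, the first factor is 9139 × 0.01³ × 0.99³⁶ = 0.00636, and with q = 0.1 the result is 0.00636 × 0.243 = 0.155%.

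| p | q = 0.1 | q = 0.2 | q = 1/3 | q = 0.5 |
|---|---|---|---|---|
| 1% | 0.155% | 0.244% | 0.283% | 0.239% |
| 2% | 0.86% | 1.36% | 1.57% | 1.32% |
| 3% | 2.00% | 3.17% | 3.66% | 3.09% |
| 5% | 4.38% | 6.92% | 8.01% | 6.76% |

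Neither p nor q is given in the documents; both are assumptions. The rationale for Amendment 1 says that severe events in healthy volunteers were few and that very few led to withdrawal, which favours the upper rows.

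**The case against.** The reading of the text is hard to dispute. The objection is about weight.

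- **Rarity.** The 3% and 5% rows imply 39 × 0.03 = 1.2 to 39 × 0.05 = 2.0 expected withdrawals of this kind in one body system, more than the stated experience suggests. This stands, and the low end should be given most weight.
- **Other oversight.** The study is single-centre and inpatient until the morning of Day 14, so the Investigator would know of all three cases. Serious events reach the Sponsor within 24 hours (Section 8.5.1). Withdrawals should be discussed with the Medical Monitor, in advance where possible (Section 7.2). Immediate safety concerns go to the Sponsor (Section 8), the Sponsor may periodically review other adverse event data (Section 8.6), and it may end the study at any time (Section 10.1.8). These make it unlikely that such a cluster goes unnoticed. They act case by case or by judgement, and none obliges the committee to convene.
- **The committee charter.** Protocol Section 9.8 and SAP Section 4.5 refer to a charter that is not available here. It might convene the committee on other grounds. The gap is shown for Section 7.1.2 only, but that section states the rules that apply.
- **Deliberate relaxation.** Amendment 1 replaced stricter first-in-human defaults. That explains higher thresholds; it does not explain why a serious case should stop counting toward three.
- **An incomplete remedy.** One serious reaction of moderate intensity, or one without withdrawal, plus two severe nonserious withdrawals would still trigger nothing after the change. This is true, but those clusters are not plainly worse than one that does trigger; each is worse on one attribute and milder on another. The change removes the one case where a strictly worse cluster is treated more leniently.

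**Conclusion.** The point holds: the rule is wrong as written for one combination, (serious, nonserious) = (1, 2). If a fourth participant is affected in the same way, the mandatory review starts then, one case late. If there is no fourth, it never becomes mandatory. Clusters with two or more serious reactions are already covered, and a review that has begun is not undone if an event is later upgraded to serious.

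The practical size is small. About 24% to 44% of three-case clusters would fall in the gap for q from 0.1 to 0.5, but such clusters are themselves rare: the overall chance is roughly 0.15% to 1.6% for p of 1% to 2%. These figures rest on assumed p and q, independence between participants, and one qualifying reaction per participant. The logical gap rests on none of the assumed rates. It does not affect the pharmacokinetic analysis. It should be corrected because the correction is simple and the rule protects healthy volunteers.

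**What to change.** In the second criterion of Section 7.1.2, replace *severe nonserious* with *severe, whether serious or nonserious,* in both the opening phrase and the parenthetical definition. Keep the threshold of 3, the same-body-system and withdrawal conditions, and the whole of the first criterion. Among clusters of severe reactions with withdrawal, only the (1, 2) case changes, so the relaxation made by Amendment 1 is otherwise preserved.

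The wording needs a protocol amendment and IRB/IEC approval (Section 10.1.1). Amendment 1, which last revised these criteria, was classed as substantial, so it is sensible to include the change in an amendment made for other reasons. In operation the cost is a rare additional internal committee review. If the committee charter repeats the criteria, it should be aligned at the same time.

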### **7.1.3        Temporary discontinuation**

If a study participant discontinues study medication, no restart will be allowed.

## **7.2           Participant discontinuation/withdrawal from the study**

Study participants are free to withdraw from the study at any time, without prejudice to their continued care.

A study participant may withdraw from the study at any time at his own request, or may be withdrawn at any time at the discretion of the Investigator for safety, behavioral, compliance, or administrative reasons.

If the study participant withdraws consent for disclosure of future information, the Sponsor may retain and continue to use any data collected before such a withdrawal of consent.

If a study participant withdraws from the study, he may request destruction of any samples taken and not tested, and the Investigator must document this in the site study records.

See the Schedule of activities (Section 1.3) for data to be collected at the time of study discontinuation and follow up and for any further evaluations that need to be completed.

Study participants should be withdrawn from the study if any of the following events occur:

1. The study participant develops a clinically relevant medical condition (physical or psychiatric) that, in the opinion of the Investigator, jeopardizes or compromises the study participant's ability to participate in the study or made it unsafe to continue.
2. The study participant is noncompliant with the study procedures or medications in the opinion of the Investigator.
3. The study participant takes prohibited concomitant medications as defined in this protocol.
4. The study participant withdraws his consent.
5. The Sponsor or a regulatory agency requests withdrawal of the study participant.

---

6. The study participant has changes in the ECG that are regarded as clinically significant and/or that worsen over time. An ECG shows an absolute value for QTcB or QTcF  $\geq 500\text{ms}$  or  $\geq 60\text{ms}$  above Baseline.

7. The study participant develops a second- or third-degree atrioventricular block or another clinically relevant change in ECG as determined by the Investigator.

8. The study participant has active suicidal ideation without a specific plan as indicated by a positive response (“Yes”) to Question 4 of the “Since Last Visit” version of the C-SSRS. The study participant should be referred immediately to a mental healthcare professional and may be withdrawn from the study based upon the Investigator’s judgment of benefit/risk of continuing the study participant in the study on PSL.

- The study participant has active suicidal ideation with a specific plan as indicated by a positive response (“Yes”) to Question 5 of the “Since Last Visit” version of the C-SSRS. The study participant should be referred immediately to a mental healthcare professional and must be withdrawn from the study.

9. The study participant is suspected of having a serious multiorgan hypersensitivity reaction. Serious suspected multiorgan hypersensitivity cases may be identified and reported to the Sponsor by the Investigator using the following algorithm:

- An AE or laboratory value (as defined below) suggestive of internal organ involvement including but not limited to hepatitis, nephritis, pneumonitis, carditis, colitis, encephalitis, pancreatitis, myositis, arthritis, or hematologic system involvement combined with at least 1 of the following: fever, rash, lymphadenopathy, or eosinophilia.
- Treatment-emergent abnormal laboratory value criteria suggestive of internal organ involvement or eosinophilia:
  - Eosinophils percentage  $\geq 10\%$ .
  - Eosinophils absolute  $\geq 5.0 \times 10^2/\mu\text{L}$ .
  - Neutrophils absolute  $< 15.0 \times 10^2/\mu\text{L}$ .
  - Platelets absolute  $\leq 10.0 \times 10^4/\mu\text{L}$ .

Withdrawn study participants should follow the taper schedule, if possible, unless faster discontinuation is considered necessary in the medical judgment of the Investigator. Investigators should attempt to obtain information on study participants in the case of withdrawal.

Investigators should contact the Medical Monitor, whenever possible, to discuss the withdrawal of a study participant in advance.

### **7.3 Lost to follow up**

A study participant will be considered lost to follow up if he repeatedly fails to return for scheduled visits and is unable to be contacted by the study site.

The following actions must be taken if a study participant fails to return to the clinic for a required study visit:

- The site must attempt to contact the study participant and reschedule the missed visit as soon as possible and counsel the study participant on the importance of maintaining the assigned

visit schedule and ascertain whether or not the study participant wishes to and/or should continue in the study.

- Before a study participant is deemed lost to follow up, the Investigator or designee must make every effort to regain contact with the study participant (at least 1 phone call and 1 written message to the study participant), and document his/her effort (date and summary of the phone call and copy of the written message in the source documents), to complete the final evaluation. All results of these evaluations and observations, together with a narrative description of the reason(s) for removing the study participant, must be recorded in the source documents. The eCRF must document the primary reason for withdrawal.

Should the study participant continue to be unreachable, he will be considered to have withdrawn from the study with a primary reason of lost to follow up documented in the eCRF.

